### **Power for Specific Aim 3 – Mediational Analysis.**

Aim 3 will involve a test of the hypothesis that the effectiveness of MBRP vs. RP on clinical outcomes is mediated by the effect of MBRP on the molecular mechanisms, and, in turn, their effects on network connectivity and BOLD response. This analysis will involve the use of structural equation modeling ([name] et al., 2007) techniques of the mediational model posited in Figure 4. Based on our review of the literature (see above for details and effect sizes), we expect moderate to large paths ( $d=.60$ ) for the effect of MBRP on epigenetics and inflammation. We expect small to moderate relationships between epigenetics and cue-elicited BOLD activation and between inflammation and network connectivity strength ( $d=.30$ ). Finally, for paths relating BOLD activation and network connectivity strength to drinking outcomes we expect paths in the small to moderate range ( $d=.30$ ). We expect moderate to large ( $d=.75$ ) loadings of all indicators for their respective latent constructs (for example, the loadings of heavy drinking days, drinks per drinking day, and impaired control on the Drinking Outcomes latent variable). Power analyses for these hypotheses were conducted in Mplus and then in SAS following procedures for estimating the power of the likelihood ratio test of the significance of parameters in structural equation models (Muthén & Muthén, 2002). We utilized Monte Carlo simulation to generate a population covariance matrix based on the hypothesized

parameters in the model. For the smallest path in the model, assuming two-tailed alpha of .05, our power to detect a significant parameter estimate is .71 with 150 participants and .83 with 200 participants; with 226 participants we have .87 power. For the moderate to large paths, we have well over .99 power with 226 participants.

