### ***Power Analysis:***

#### **Sample Size Requirements.**

Sample size was selected to permit analysis of the hypotheses at a two-tailed alpha of .05 and power level of at least .80 following Cohen (Cohen, 1988). G\*Power 3.0.3 (Erdfelder, Faul, & Buchner, 1996) was utilized for some power calculations, while Monte Carlo simulation strategies formed the basis of our power analysis for the mediational model ([name], Schmiege, & Broaddus, 2007; Mackinnon & Dwyer, 1993).

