#### **The impact of attrition.**

It is anticipated that some attrition will occur in this population, though we do not anticipate differential attrition by condition. A conservative estimate of 20% attrition over the course of data collection is assumed. Recently published evidence suggests an attrition rate of approximately 20% for other trials. In our own previous trials, we have seen attrition of around 20%. Thus, sample size will need to be increased by 20% over minimum requirements. After final attrition has been calculated, pretest differences on alcohol use and problems will be compared among individuals who finished the study versus those who did not and by condition, to determine whether these two groups differed in

systematic ways and whether these differences were related to treatment condition.

With respect to attrition during the follow-up period, all participants will update their address and phone number as well as the name and number of an individual who always knows how to reach them at every visit. The project coordinator will also contact each patient in between follow-up visits.

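### Aim 3 power is headlined as .87 at all 226 recruits; at the roughly 181 completers the plan expects, its own figures give about .79, just under the .80 target

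*Combined protocol and SAP*

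**What the plan says.** Sample Size Requirements says the sample was chosen to give a "power level of at least .80" for the hypotheses, at a two-tailed alpha of .05.

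The impact of attrition says: "A conservative estimate of 20% attrition over the course of data collection is assumed". It adds that the sample must be enlarged over the minimum to allow for this. Power for Specific Aim 1 does so: power is computed at 180 participants, and about 226 are to be recruited.

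Power for Specific Aim 3 works differently. Its smallest paths are .30: methylation to BOLD, inflammation to connectivity, and each brain measure to drinking. Treatment paths are .60 and loadings .75, and all of these are labelled *d*. The power comes from Monte Carlo simulation of a structural equation model. The results are: "our power to detect a significant parameter estimate is .71 with 150 participants and .83 with 200 participants", and then "with 226 participants we have .87 power". No figure is given near 180, and the section does not say that the simulated data contained missing values.

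**The concern.** The two power sections use different bases for N. Aim 1 is powered on those expected to remain after attrition, Aim 3 on everyone recruited. A reader who takes .87 as the power of the mediation analysis will think it has a comfortable margin over .80. With the plan's own attrition rate there is none.

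This bears on interpretation. Aim 3 is a named specific aim, and the plan says it is worth testing even if the arms do not differ on drinking. A non-significant path would be read against the stated power. If that power is overstated, a null path looks more informative than it is.

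**Working it through.** **Inputs.** Two-tailed alpha .05; stated power .71, .83 and .87 at N = 150, 200 and 226 (Power for Specific Aim 3); attrition 20% (The impact of attrition); target .80 (Sample Size Requirements).

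**Step 1: do the three figures lie on one curve?** For a test of one parameter, power is approximately Φ(e√N − 1.960), where e is the effective standardised effect. Solving, e = (1.960 + z_power)/√N:

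- N = 150: (1.960 + 0.553)/12.247 = .2052
- N = 200: (1.960 + 0.954)/14.142 = .2061
- N = 226: (1.960 + 1.126)/15.033 = .2053

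They agree to within rounding, with mean e = .2055. Putting .2055 back returns .71, .83 and .87, so the plan's figures are reproduced and can be interpolated. Here e summarises the plan's simulation output; it is not an estimate of any path coefficient.

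**Step 2: power at the expected completers.** 226 × 0.8 = 180.8, about 181.

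- N = 180: .2055 × 13.416 − 1.960 = 0.797, power .787
- N = 181: .2055 × 13.454 − 1.960 = 0.805, power .790

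Using the lowest and highest e (.2052 and .2061) gives .788 to .792 at 181.

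**Step 3: N for .80.** N = ((1.960 + 0.842)/.2055)² ≈ 186. Out of 226, that allows a loss of 40, or 17.7%. With 20% loss, recruitment would have to be 186/0.8 ≈ 233.

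**Step 4: participants with scans.** Every .30 path has BOLD or connectivity at one end. Scans are done only in eligible participants (MRI Data Collection; Follow-up Assessment II), who may opt out (Exposure to Alcohol, under Management of Risks). The remote version of the study collects no MRI or blood. The documents do not give the share scanned, so the range below is an assumption:

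| Share of 181 with usable scans | N | Power on the plan's curve |
|---|---|---|
| 100% | 181 | .79 |
| 90% | 163 | .75 |
| 80% | 145 | .70 |
| 70% | 127 | .64 |

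**The case against.** Four points can be made for the plan.

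- **Nothing is hidden.** The values at 150 and 200 are printed, and a reader can see that 181 falls between them. That is true, but the closing figure is .87, and the section never relates it to the attrition assumption.
- **Missing data are handled by FIML.** The Data Analysis Plan specifies it within EQS, so partial records contribute and a completer count is somewhat pessimistic. The drinking outcome in this model is also taken at 20 weeks, before all of the 20% loss need have occurred. This stands in part. But FIML recovers little for a path whose brain measure is missing, and essentially nothing when both ends are missing, as for remote participants. Section IV places the second scan at week 32, so that measure bears the full attrition.
- **The interpolation is not the simulation.** Agreed. It shows where the plan's curve lies, and the rerun should supply the reported number.
- **The scanned share is unknown.** Agreed. The lower rows of the table are illustrations, not estimates.

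A reader might go further and infer that .71/.83/.87 cannot come from paths of .30 at all, because simple two-variable formulas do not return them. The documents do not support that. The figures come from a latent-variable simulation, where measurement error and the choice of estimated paths change the power for a given coefficient. In that section *d* also labels factor loadings, so it cannot mean a two-group standardised difference throughout. A model with standardised .30 paths, loadings of .75, connectivity latent with two indicators and cross-paths estimated gives .70/.82/.86 at the same three sample sizes, and .776 at 180. With only methylation, inflammation and drinking latent, as the Aim 3 analysis text has it, three indicators each and no cross-paths, the result is .92/.97/.99, which is higher than stated. The inputs in the text do not fix the answer, but they do not contradict it. The model diagram (Figure 4) is not visible in the text reviewed and is not counted as missing.

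**Conclusion.** The stated Aim 3 power is wrong as written, with minor severity. At the completers the plan expects, its own curve gives about .79, not .87: about eight points below the headline and about one point below the .80 target. This assumes the 20% attrition rate, a single power curve through the three printed values, and completers as the effective sample. FIML could raise the figure slightly; incomplete scanning and remote participation could lower it by more, by an amount the documents do not allow one to fix.

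**What to change.** In Power for Specific Aim 3:

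1. State the .30 paths and .75 loadings as standardised coefficients instead of *d*, and give the simulated population model (indicators, residual variances, estimated paths).
2. Rerun the existing simulation at about 181 and at the expected number with both scans and blood, stating the assumed share. If credit is wanted for FIML, build the missingness into the simulated data.
3. Report that result as the Aim 3 power in place of .87. On the current curve it is about .79 at 181.

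The cost is one rerun and a slightly less favourable stated power. Design and analysis are unchanged.

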### **Specific Aim 3 - Mediational analyses.**

Mediational analyses based on structural equation modeling with latent variables will be used to examine the mechanisms by which MBRP has its effects on behavioral outcomes related to alcohol use and dependence (See Figure 4; HYPOTHESIS 4) (Baron & Kenny, 1986; [name] et al., 2007). Mediational analyses will utilize the methylation and inflammation data collected at 4 weeks, and changes in cue-elicited BOLD activation and network connectivity strength at 8 weeks as the mediators, and drinking outcome data collected at 20 weeks. The exogenous variable in the model is the contrast that compares MBRP to RP. Methylation, inflammation, and drinking outcomes are all conceptualized as latent variables, which means that they are not directly measured, but are rather inferred via the measurement of variables thought to be a consequence of the latent variable. Latent variables have advantages over measured variables in that they are more reliable and thus allow for higher power for the test of relationships between the underlying construct and other variables (Kline, 2010).

The model is then estimated in EQS, and both the fit of the model and the significance of the path coefficients are examined. If HYPOTHESIS 4 is supported, we will see significant paths from the treatment contrast to methylation and inflammation. Further, there will be significant paths from methylation to cue-elicited BOLD activation and from inflammation to network connectivity. Finally, we expect significant relationships between BOLD activation and network connectivity to drinking outcomes. Importantly, tests for the completeness of mediation of the treatment differences in drinking outcomes are employed through a one degree of freedom  $\chi^2$  test where a path directly from the treatment contrast to drinking outcomes is added to the model. A nonsignificant direct path and a nonsignificant change in  $\chi^2$  suggest that treatment effects on drinking outcomes were mediated through the series of molecular and brain-based mechanisms. A secondary test of mediation will utilize bootstrap methods to test the significance of, and confidence limits around, the mediated effect (Mackinnon & Dwyer, 1993). Similar mediational analyses have been widely used by Co-I [name] ([name] et al., 2007).

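### Aim 3's stated power of .87 covers one path; for the six significant paths that the plan ties to Hypothesis 4, its own inputs imply roughly .56 to .61 at 226, and no such figure is given.

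*Combined protocol and SAP*

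**What the plan says.** Under Sample Size Requirements, the sample size is said to allow the hypotheses to be tested at a "two-tailed alpha of .05 and power level of at least .80".

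Power for Specific Aim 3 – Mediational Analysis then gives the power from a Monte Carlo simulation. The key sentence opens "For the smallest path in the model, assuming two-tailed alpha of .05" and reports .71 at 150 participants and .83 at 200, ending "with 226 participants we have .87 power". It is followed by "For the moderate to large paths, we have well over .99 power with 226 participants". The assumed sizes are in the same section: "we expect moderate to large paths ( $d=.60$ ) for the effect of MBRP on epigenetics and inflammation". The four remaining structural paths are each given d=.30: methylation to BOLD, inflammation to connectivity, BOLD to drinking, and connectivity to drinking.

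In the Data Analysis Plan, Specific Aim 3 - Mediational analyses states: "If HYPOTHESIS 4 is supported, we will see significant paths from the treatment contrast to methylation and inflammation". It continues: "Further, there will be significant paths from methylation to cue-elicited BOLD activation and from inflammation to network connectivity". A third sentence adds that significant relations of both BOLD activation and connectivity with drinking outcomes are expected. That makes six paths. The section also plans a one-degree-of-freedom chi-square test for completeness of mediation, and a bootstrap test of the mediated effect, which it calls secondary.

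The Objectives (Specific Aim 3) state Hypothesis 4 as one hypothesis with two routes, one through inflammation and connectivity and one through methylation and BOLD.

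**The concern.** The .87 is the main power figure in the section on Aim 3, next to a general statement of at least .80 for the hypotheses. A reader will naturally take it as the chance of confirming Hypothesis 4 if the mechanism is true. But the plan describes a confirmed Hypothesis 4 as several significant results at once, and the power for a set of results is lower than for any one of them. No power is given for the set, for one route, or for the mediated effect.

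What is at stake is interpretation. The plan regards the Aim 3 test as critical even if the two treatments do equally well on drinking. If five of six paths are significant and one is not, a reader relying on .87 may take the miss as evidence against the mechanism, when under the plan's own assumptions such a miss would be common.

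**Working it through.** **Inputs, all from the combined protocol and SAP**

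- Single-path power, two-tailed alpha .05: .71 at 150, .83 at 200, .87 at 226 (Power for Specific Aim 3).
- Power for the two treatment paths: well over .99 at 226; .99 is used below (same section).
- Four paths at d=.30 and two at d=.60 (same section).
- Attrition 20% (The impact of attrition). The Aim 1 power section works with 180 participants; 226 × .80 = 181.

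**Step 1. Check the plan's own figures.** For a two-sided one-degree-of-freedom test, power ≈ Φ(k√N − 1.96), so k = (1.96 + z_power)/√N.

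| N | stated power | k |
|---|---|---|
| 150 | .71 | (1.96 + .553)/12.247 = .205 |
| 200 | .83 | (1.96 + .954)/14.142 = .206 |
| 226 | .87 | (1.96 + 1.126)/15.033 = .205 |

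The three figures agree with one effect. They could not be derived afresh from d=.30, because the path diagram (Figure 4) is not shown and the scale of d for a path is not defined. The rest therefore accepts .87 as given. With k = .2053, single-path power at 180 is Φ(.2053 × 13.416 − 1.96) = Φ(.794) = .787.

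**Step 2. All six paths, assuming independent tests and equal power for the four d=.30 paths.**

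- N=226: .87⁴ = .573; × .99² = .56.
- N=180: .787⁴ = .383; × .99² = .375. Using d=.60 with 90 per arm for the treatment paths instead of .99 gives .368.

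**Step 3. One complete route (one treatment path, two small paths).**

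- N=226: .99 × .87² = .75.
- N=180: .99 × .787² = .61.

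**Step 4. Check by simulation.**

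- An observed-variable path model (6,000 runs, d=.60 for the treatment paths, standardized .205 for the four small paths) gave .88 and .80 for a single path at 226 and 180. One route came to .77 and .64, and all six paths to .61 and .41.
- A latent-variable model with small paths of about .23 (power .88 to .89 each at 226) gave .56 and .35 for all six. Its two treatment paths had .975 at 226 and .94 at 180, a little below the plan's figure. Correlations between path estimates were at most .06 in size, and the joint power matched the product to within .001.

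**Step 5. Relax the assumptions, at N=226.**

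- Only three paths at .87 and the fourth near 1: .87³ × .99² = .65.
- Only two at .87: .87² × .99² = .74 (.76 without the treatment paths).
- No independence assumption, all four at .87: lower bound 1 − 4(.13) − 2(.01) = .46; upper bound .87.
- Also requiring a nonsignificant direct path lowers the Step 2 results by about 5% in relative terms, to about .53 at 226 and .36 at 180.

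**The case against.** The strongest reply is that no stated number is wrong. The .87 is labelled as the smallest path's power, and the three quoted powers agree with each other. That stands: what is missing is a further quantity, and nothing here shows .87 to be miscalculated.

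A reader might go further and infer that the trial would declare Hypothesis 4 unsupported about 40% of the time at 226 and 60% at 180 even if the mechanism held. The documents do not support that. The analysis section describes the pattern expected if the hypothesis is supported; it is not a formal decision rule. The sentence on the last two paths states only an expectation. No sentence says that one nonsignificant path defeats the hypothesis, and a bootstrap test of the mediated effect is also planned. What remains is that six significant paths is the only description of support given, and no power is attached to it.

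Equal power for the four d=.30 paths is an assumption. The same d need not give the same power in a model mixing latent and other variables, so a range is more honest than a single value. Even with only two paths at .87, the joint figure stays below .80. The upper bound of .87 needs almost complete dependence between tests, which the model check does not show.

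The 180 is borrowed from Aim 1. The planned full-information likelihood can retain partial cases, which argues for a larger effective number. In the other direction, all four small paths involve a brain measure, scanning is limited to eligible participants who may opt out, and the remote phase collects neither MRI nor blood. The figures at 180 are approximate either way.

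Finally, heavy drinking days is the primary outcome and the recruitment target is derived under Aim 1. Requiring every path to be significant is conservative and inflates no false-positive claim. That limits the seriousness of the point.

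**Conclusion.** The point holds as a gap in the power statement for a mechanistic aim, and should be fixed. The plan's general statement of at least .80 is not shown for Hypothesis 4, and its own inputs do not deliver it for the six-path pattern.

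If the four d=.30 paths each have .87 power and the tests are nearly independent, joint power is about .56 to .61 at 226, and about .35 to .41 if 180 contribute. With fewer paths at .87 it rises to about .65 (three) or .75 (two). Requiring only one complete route gives about .75 to .77 at 226 and .61 to .64 at 180, so that reading also misses .80. The one-route figures are for three significant paths together; power for the bootstrap mediated effect would need its own simulation.

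The primary drinking analysis is not affected.

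**What to change.** - In Power for Specific Aim 3, keep .87 as the single-path figure. Re-run the existing Monte Carlo programme to add the power for each route's indirect effect and for all six paths together, at 226 and at the number expected to contribute after attrition.
- In Sample Size Requirements, limit the .80 statement to the tests that reach it.
- In Specific Aim 3 - Mediational analyses, say whether a claim of support needs one route or both, and how a single nonsignificant path will be interpreted.

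Moving the bootstrap test from secondary to primary is a debatable change to the order of tests and is not needed here. The cost is one simulation re-run, a few sentences, and a less favourable stated power. The change discloses the shortfall and does not remove it. No extra participants are required.

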#### ***Data Analysis Plan:***

Analyses will be conducted using SAS Version 9.3 and EQS for Windows Version 5.7b. We will conduct extensive analyses of any attrition encountered in the project to determine bias. However, note that in each of the analyses described herein, we will have the capability of using modern approaches to the handling of missing data (Schafer & Graham, 2002) including full information maximum likelihood (FIML) estimation of missing data within Proc Mixed in SAS and within EQS.

Descriptive analyses. The distributional properties of all continuously scaled variables will be examined for skewness and kurtosis to determine the need for normalizing transformations or for alternations to our analysis plan (i.e., generalized estimating equations in SAS or robust estimation in EQS) prior to the primary analyses.

Pretest equivalence. To confirm the validity of random assignment, pretest equivalence of the two treatment conditions across demographics, drinking history, smoking, and all other baseline measures will be assessed via t-tests on continuous items and  $\chi^2$  tests of categorical items. We will use the Bonferroni approach (Keppel, 1991) to correct for alpha inflation with a familywise alpha of .05. Any variables on which the two groups are unequal at pretest will be covariates in all further analyses.

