### **Power for Specific Aim 1 - Detecting Treatment Effects on Alcohol Use Outcomes.**

The analyses of treatment effects will proceed via random coefficient regression utilizing a 2 (**Treatment**: 8 weeks of MBRP vs. 8 weeks of RP) x 5 (**Time**: Baseline, 4, 8, 20, 32 weeks) mixed general linear model. The primary outcome variable tested will be heavy drinking days (HDD), consistent with previous MBRP trials ([name] et al., 2014). Secondary analyses will explore related outcomes such as drinks per drinking day, scores on the ICS, and liver function tests, with appropriate control of Type I error. In each model, the key effect of interest will be the treatment X time interaction. Given the effect sizes in previous trials (small  $d=.23$  or  $f<.10$  to moderate  $d=.45$  or  $f=.20$ ), we conservatively estimate a small effect size (e.g.,  $f=.10$ ). A mixed model testing the between (treatment) X within (time) subjects interaction with a total of 180 participants (90 per treatment group) will give us well over .90 power, assuming alpha of .05 and a correlation of approximately .50 between repeated assessments. Given that we expect 20% attrition over the course of the trial, we will initially recruit ~226 participants.

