#### **Specific Aim 1 - Detecting Treatment Effects on Drinking Outcomes.**

The effect of the treatment on alcohol use outcomes (HYPOTHESIS 1) will be analyzed with a 2 (**Treatment:** 8 weeks of MBRP vs. 8 weeks of RP) x 5 (**Time:** Baseline, 4, 8, 20, 32 weeks) mixed general linear model with Heavy Drinking Days (HDD) as the primary outcome variable. We will also examine drinks per drinking day, ICS score, and liver function tests as dependent measures in each of 2 additional models, respectively. In the main analysis with HDD, a significant overall test of the treatment X time interaction will be followed by planned contrasts within the mixed model that allow us to test the superiority of MBRP over RP at the 8, 20, and 32 week follow-up points specifically. The FIML estimation procedure implemented in these analyses will allow us to utilize an “intent to treat” approach such that all subjects who are randomized will be included in the analyses (Schafer & Graham, 2002). It may be that the treatments are equally effective on drinking outcomes, and thus we will not see a direct effect of treatment on outcomes. Even in this case, it is possible that the mechanisms through which the treatments had their impact may differ. Thus, tests of Specific Aims 2 and 3 are still important and warranted.

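### For skewed heavy drinking days the plan allows GEE with no decision rule and no missing-data method, so the FIML basis of its intent-to-treat claim would not carry over

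*Combined protocol and SAP*

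**What the plan says.** The opening of the Data Analysis Plan says the analyses will be able to use modern missing-data methods, including "full information maximum likelihood (FIML) estimation of missing data within Proc Mixed in SAS" and in EQS. The paragraph on descriptive analyses then has skewness and kurtosis examined. It offers two responses: a transformation toward normality, or "alternations to our analysis plan (i.e., generalized estimating equations in SAS or robust estimation in EQS) prior to the primary analyses". It gives no threshold and no order of preference. For GEE it names no link, working correlation, weighting or imputation.

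The Specific Aim 1 analysis section makes HDD the primary outcome in a 2 x 5 mixed model. It credits the FIML procedure with permitting an intent-to-treat approach, "such that all subjects who are randomized will be included in the analyses". The contrasts at weeks 8, 20 and 32 are defined inside that mixed model.

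Three other places bear on this:
- The impact of attrition (Power Analysis) assumes 20% attrition, with none expected to differ by condition.
- Differential attrition analyses tests treatment by retention on baseline measures only.
- Baseline Session (Procedures) requires a breath test before every session. A repeat positive test the next day makes a session count as missed, and more than one missed session removes the participant from the study.

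**The concern.** HDD comes from a 30-day Timeline Follow Back, so it is bounded at 0 and 30. Abstinence is encouraged, though not required. A cluster of zeros and a skewed distribution are therefore foreseeable, and a monotone transformation cannot remove a spike at zero. GEE could well be taken up.

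FIML in a mixed model gives valid estimates when dropout depends on drinking already recorded, provided the model is right. Standard GEE is not a likelihood method and in general needs the stronger condition that dropout does not depend on earlier outcomes. The plan's missing-data argument therefore covers one of its two permitted routes and is silent on the other.

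The breath-test rule ties removal from the study to drinking, at least in the in-person protocol; the remote schedule lists no breath tests. The attrition checks compare baseline characteristics, so they would not show that people left because of drinking after baseline. At stake are the primary treatment comparison and the trial's stated basis for calling it intent-to-treat.

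**Working it through.** **1. The plan's own figures.** Inputs from the sample-size and Aim 1 power sections: "two-tailed alpha of .05 and power level of at least .80"; "we conservatively estimate a small effect size" of f = .10 (d about .20, since f = d/2 for two equal groups); "a total of 180 participants (90 per treatment group) will give us well over .90 power"; "a correlation of approximately .50 between repeated assessments"; and "Given that we expect 20% attrition over the course of the trial, we will initially recruit ~226 participants".

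- Noncentrality = f² x N x m / (1 − rho) = .01 x 180 x 5 / .5 = 18, with 4 and (180 − 2) x 4 = 712 degrees of freedom. Power = .942, which agrees with the plan.
- Recruitment = 180 / .80 = 225, against about 226 stated.

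The planning figures reproduce, and the point does not depend on an error in them.

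**2. What GEE might do to the week-32 difference.** The documents give no HDD mean, SD, zero fraction or dropout model, so everything below is assumed. In all settings 20% of each arm is lost by week 32, with the dropout hazard depending on the last observed value.

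- *Normal outcome:* 400,000 per arm, d = .20 to .45, correlation .5 at all lags or autoregressive .7, log-odds of dropout up to 2 per SD with equal dependence and up to 1 per SD otherwise.
- *Skewed counts capped at 30:* 60,000 per arm, means 14, 8, 7, 7, 7 before capping with a smaller mean in MBRP, average correlation about .48, log-odds .1 or .2 per heavy drinking day.

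Shift = GEE difference / true difference − 1, at d about .20 to .23 (percentages taken before rounding):

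| Drinking-dropout relation | Outcome | Independence | Exchangeable |
|---|---|---|---|
| Same in both arms | Normal | 0 to 5% | 0 to 5% |
| Same in both arms | Skewed | 11 to 16% | 1 to 2% |
| One arm only | Normal, correlation .5 or AR .7 | about −50% to +51% | 0 to 11% |
| One arm only | Skewed | −44% (RP), +34% (MBRP) | 0 to 4% |
| Opposite in the two arms | Normal | 46 to 99% | up to 23% |
| Opposite in the two arms | Skewed | 59% | 3% |

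Examples with skewed counts:
- Dependence in RP only: true −1.57 days, independence −0.89, exchangeable −1.51.
- Dependence in MBRP only: true −1.53, independence −2.04, exchangeable −1.53.
- Same dependence in both arms (.2 per day): true −1.58, independence −1.33, a shift of 1.33/1.58 − 1 = −16%.

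**3. Why the percentage depends on the effect size.** For the normal outcome with correlation .5 and one-arm dependence of 1 log-odds per SD, independence moves the difference by about .10 SD whatever the true effect. That is .10/.20 = 50% at d = .20 and .10/.45 = 22% at d = .45. Likelihood estimation on the same normal data stayed within about 4%, which is simulation noise.

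**The case against.** The strongest reply is that the plan does not commit to GEE. A transformation is listed first and would keep Proc Mixed and FIML. This stands: a reader might infer that skewness forces GEE, and the text does not say so. The opening of the Data Analysis Plan also describes FIML as a capability within a non-exclusive list. That is true, but the Aim 1 section does rest the HDD intent-to-treat statement on FIML.

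A reader might also infer that GEE would exclude randomized participants. It would not. Baseline is one of the five time points, so anyone with a baseline record contributes. What is lost is validity when dropout depends on earlier drinking.

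Nor do the documents support a reading that drinking-related dropout by itself shifts the effect by about half. That needs an independence working correlation, which the plan does not specify, and a relation that differs by arm. The plan expects no differential attrition by condition. That expectation, however, concerns how many leave. In the simulations both arms lose 20%, and the larger bias comes from a difference in who leaves.

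Finally, the planned attrition analyses are a genuine safeguard against imbalance in baseline characteristics. They do not examine drinking after baseline.

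**Conclusion.** The concern holds as a gap in specification. The plan permits GEE for its primary outcome without saying when it applies, how it is set up or how it handles dropout, and its FIML argument does not extend to that route.

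The size is uncertain and mostly modest. At d about .2, expect 0-5% (normal) or 1-16% (skewed counts) if dropout depends on drinking alike in both arms. Expect 0-11% with an exchangeable correlation and dependence in one arm. A shift of about 35-50% needs independence together with one-arm dependence, and at d = .45 the corresponding figure for the normal outcome is 10-22%. These are scenario results, not typical values and not a ceiling: opposite relations in the two arms gave more. All rest on assumed distributions and dropout strengths. No bias arises from this source if the transformation route is taken and the mixed model is adequate, or if dropout is unrelated to drinking.

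**What to change.** In the descriptive-analyses paragraph of the Data Analysis Plan, replace unweighted GEE as the HDD fallback with one of two options:
- a likelihood-based model that relies on the same missing-at-random assumption as the mixed model, for example a beta-binomial model for heavy drinking days out of 30 with a random subject effect, fitted by full maximum likelihood; or
- GEE used only after multiple imputation or with dropout weights, with the link and working correlation named.

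State the rule for choosing between the transformation and this fallback, and settle the choice before outcome data by arm are examined. In the Specific Aim 1 section, restate the week 8, 20 and 32 contrasts for the fallback model and say which missing-data method supports the intent-to-treat statement. It is not necessary to fix an untransformed linear model regardless of skewness; that is a matter of preference.

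The cost is a paragraph of text and one extra model or imputation step, with no new data. The drawback is that a count-model effect must be converted back to days for reporting.
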